**Effectiveness of additional thoracic paravertebral block in
improving anesthetic effects of regional anesthesia for
proximal humeral fracture surgery in elderly patients**

Study Protocol

2019.3.21

Principle Investigator: [name]

Co-Investigator: [name]

[name]

[name]

[name]

[name]

[name], PhD

[name], PhD

Objective

To investigate whether supplementary T2 thoracic paravertebral block (TPVB) could improve the anesthetic effect of cervical-brachial plexus block based regional block.

Background

Proximal humeral fractures (PHF) is a common disease occurring in the elderly population over 60 years. The deltopectoral approach is commonly used in the PHF surgery. The innervation of PHF surgical area is complicated and unclear. Ultrasound-guided brachial plexus combined with cervical plexus block is probably inadequate for the anesthesia of proximal humeral surgery. Missing blockade of T1-T2 nerves may be the reason. The primary aim of this trial is to investigate the effectiveness of additional T2 thoracic paravertebral block (TPVB) in improving the anesthetic effects of regional anesthesia for elderly patients in proximal humeral fracture surgery.

Methods

We have designed a two-armed, parallel, randomized controlled trial (RCT) to observe the anesthetic effects of ultrasound-guided brachial and cervical plexus block with or without additional T2 TPVB in terms of the following outcomes: success rate, sensory block and safety. The elderly patients aged 65 or older, referred for anterior approach proximal humeral fracture surgery, will be enrolled. Each participant will be randomly assigned 1:1 to receive IC block (combined interscalene brachial plexus with superficial cervical plexus block) or ICTP block (combined thoracic paravertebral block with IC block). The primary outcome is the success rate of surgical anesthesia. The secondary outcomes are as follows: sensory block at surgical area, proportion of participants who need supplementary anesthesia (intravenous remifentanyl or conversion to general anesthesia), cumulative doses of intraoperative vasoactive medications and adverse events. The necessary sample size is estimated to be 80.

Randomization and blinding

Random allocation will be performed by a researcher (HZ) before the trial using a randomization sequence. The allocation concealment strategy is achieved with sequentially numbered, opaque, sealed envelopes to conceal the sequence until the intervention is assigned. The envelopes will be opened sequentially before the nerve block is performed. Participants will be randomly assigned in a 1:1 ratio to receive IC block or ICTP block. As the nerve block intervention cannot be blinded from participants and staff implementing the intervention, only the outcome assessor and data statistician will be kept blinded to the randomized allocation and intervention. The envelope will be resealed after confirming the allocation.

Interventions

All the participants will undergo preoperative fasting for 8 hours and water deprivation for 2 hours. After placement of standard ASA monitors, intravenous access for fluid infusion will be established in the forearm. No sedatives or analgesic medication will be given prior to the block. The participant will receive ultrasound-guided IC block or ICTP block according to the allocation. It will be performed following standard skin disinfection with a SonoSite S-Nerve™ ultrasound machine (Bothell, WA, USA). The entire nerve block procedure of all the participants will be performed by the same anesthesiologist, who is skilled in performing ultrasound-guided regional anesthesia.

In the IC group, the procedure will be performed as followed.

The participant will be placed in the lateral decubitus position with the operative side upwards. A linear array transducer (6-13 MHz) with a sterile cover and a 22G (gauge) block needle will be used. An in-plane approach, advancing the needle along the longitudinal axis of the transducer and visualizing the entire shaft, will be employed. Twenty ml of 0.375% ropivacaine will be injected between superior and middle trunk of brachial plexus at C7 level to reduce phrenic nerve palsy. The transducer will be then moved cephalad until the superficial cervical plexus emerges from the C4 intervertebral foramen. Ten ml of 0.25% ropivacaine will be injected to block the nerve.

In the ICTP group, the procedure will be performed as followed.

On the basis of IC block, T2 TPVB will then be performed. The T2-T3 intervertebral space should be determined by ultrasound image scanning and palpation counting from C7 spinous process. A curve array transducer (2-5 MHz) will be placed at the T2-T3 intercostal level with a slightly oblique scan to visualize the transverse process, costotransverse ligament, internal intercostal membrane and parietal pleura. A 10cm, 22G needle will be introduced into the thoracic paravertebral space beyond the internal intercostal membrane with its tip positioned outside the transverse process. Following negative aspiration of air, blood or cerebrospinal fluid in the needle, 10 ml of 0.25% ropivacaine will be injected into the paravertebral space.

Then the participant will be placed in the supine position. Twenty minutes later, after the sensory block assessed, the participant will be transferred to the operating room and placed in a beach-chair position. One mg midazolam will be given intravenously. Oxygen will be routinely given via a nasal catheter at the flow rate of 3L/min until the end of operation. In case of inadequate analgesia, remifentanil (50 μ g/ml), propofol (10mg/ml) and laryngeal mask airway (LMA) insertion will be prepared. The anesthetic effects will be assessed since the operation begin: 1) if it is successful, the operation will be continued; 2) if it is failed, the operation will be paused and remifentanil will be given intravenous at the rate of 0.25 μ g/kg/min. Two minutes later, the operation will be continued if the participant is satisfied with the anesthetic effect. The rate of intravenous remifentanil can be appropriately regulated (no more than 0.25 μ g/kg/min) in the following operation according to the P_{ET}CO₂ and respiratory rate of the participant. On the contrary, the intolerable participant will be induced with propofol (1.5-2 mg/kg) for converting to GA with LMA. The participant who received GA will be transferred to post-anesthesia care unit (PACU) after the operation.

Statistical analysis plan

Primary analyses will be undertaken on an intention-to-treat basis, including all participants as randomized, except those who withdraw consent for the use of their

data. Data will be expressed as mean \pm standard deviation (SD), median (interquartile range), or percentage. Continuous variables will be analyzed with a two-sample t test with equal/unequal variance or with a Mann and Whitney U test, if appropriate. A chi-square test or Fisher's exact test will be used for categorical variables. The statistical analysis will be performed using SPSS V.24.0 (IBM Corporation, Armonk, New York, USA) with a significance level of 0.05.

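### Does the missing definition of adverse events, with PACU the only post-operative step named, undermine the safety comparison?

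*Combined protocol and SAP*

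**What the plan says.** The Methods section describes the comparison "in terms of the following outcomes: success rate, sensory block and safety". The secondary outcomes listed there end with "cumulative doses of intraoperative vasoactive medications and adverse events". The word for the intraoperative period stands before the vasoactive drugs, and the sentence does not settle whether it also limits the adverse events.

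Hazards are mentioned under Interventions, but as part of technique. The brachial plexus injection is placed "at C7 level to reduce phrenic nerve palsy", and the paravertebral injection is made "Following negative aspiration of air, blood or cerebrospinal fluid in the needle". Neither becomes a listed event.

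The last time point that applies to everyone is the end of surgery: "Oxygen will be routinely given via a nasal catheter at the flow rate of 3L/min until the end of operation". After that there is one sentence: "The participant who received GA will be transferred to post-anesthesia care unit (PACU) after the operation".

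Under Randomization and blinding, "only the outcome assessor and data statistician will be kept blinded to the randomized allocation and intervention". The Statistical analysis plan compares the arms as randomized with generic tests. For categorical data these are chi-square or Fisher's test, with no rule for choosing between them. It does not mention safety separately.

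**The concern.** Three features together suggest a defect.

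- **No definition.** Two analysts could each follow the plan and count different events, because neither the types nor the start and stop times are written down.
- **Observation that may depend on outcome.** The only post-operative location named is PACU, and only after GA. GA is reached when the block fails and remifentanil does not suffice. The Background expects the comparator block to be inadequate more often, so conversion should be commoner in the IC arm. If post-operative events were recorded only in PACU, the IC arm would be watched more closely, and harms of the additional block would be under-counted in the ICTP arm.
- **Small numbers.** With 40 per arm, one event inside or outside an unstated window can move a p-value across 0.05.

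At stake would be the safety statement about an extra needle procedure near the pleura in patients aged 65 or older.

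**Working it through.** **Inputs from the document:** 80 participants, 1:1, hence 40 per arm; significance level 0.05; chi-square or Fisher's test. The document gives no event rate and no conversion rate, so every such figure below is an assumption. It also states no safety figure that could be reproduced.

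**1. Sensitivity of the test to one event.** For k events against none, with 40 per arm, the two-sided Fisher p-value is 2 × C(40,k) / C(80,k).

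- k = 6: 2 × 3,838,380 / 300,500,200 = 0.0255
- k = 5: 2 × 658,008 / 24,040,016 = 0.0547

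So Fisher's test crosses 0.05 between five and six events. The plan equally allows chi-square. Without continuity correction the statistic is 80 × (40k)² / (40 × 40 × k × (80 − k)).

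- k = 5: 80 × 40,000 / 600,000 = 5.33, p = 0.021
- k = 4: 80 × 25,600 / 486,400 = 4.21, p = 0.040
- k = 3: 80 × 14,400 / 369,600 = 3.12, p = 0.077

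Under chi-square, 5 against 0 is significant and the crossing lies between three and four. Expected counts of 2.5 per arm at k = 5 make Fisher the usual choice. Either way, a discrete test has some count at which one event matters, and writing down a window would not remove it.

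**2. What zero events would show.** The exact two-sided 95% upper limit for 0/40 is 1 − 0.025^(1/40) = 0.088. This too follows from 40 per arm and not from the missing definition.

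**3. Possible distortion between arms.** Let q be the true post-operative event rate (the same in both arms), c the GA conversion rate, and d the share of events found outside PACU. If every event in PACU is found, the recorded rate is q × [c + (1 − c) × d]. The difference between arms is then q × (c_IC − c_ICTP) × (1 − d).

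| q | c, IC vs ICTP | d = 0 | d = 0.5 | d = 1 |
|---|---|---|---|---|
| 10% | 20% vs 5% | 2.0% vs 0.5% | 6.0% vs 5.25% | 10% vs 10% |
| 10% | 40% vs 10% | 4.0% vs 1.0% | 7.0% vs 5.5% | 10% vs 10% |

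At q = 10% the difference runs from 0 to 3 percentage points. It scales with q. For conversion of 40% against 10% and d = 0, it is 0.02 × 0.30 = 0.6 points at q = 2% and 0.20 × 0.30 = 6 points at q = 20%. The 40% against 10% row is also generous, because Interventions puts a remifentanil step between block failure and GA, so conversion should be rarer than failure.

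**4. Does the document imply d < 1?** The PACU sentence sits under Interventions and tells staff where a patient goes after GA. It does not say that events are recorded there, or that participants who did not need GA go unobserved. The outcome assessor is defined for the whole trial, with no link to PACU. Nothing in the text fixes d at any value below 1, so the distortion is possible but not shown.

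**The case for a change.** The strongest case for acting is that the omission is complete and the intervention is invasive. The document is short, nothing appears to be blacked out at this point, and it still lists no event, although it shows awareness of phrenic nerve palsy and of air, blood or cerebrospinal fluid on aspiration. A definition would cost one paragraph and one form, with no change to sample size or treatment. Without it, the choice of window could be made after the data are seen.

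Much of this stands. The definition is absent, a written list would be better practice, and its cost would be small. The document does not exclude a choice made late, although the outcome assessor and the statistician are both blinded to allocation, which limits the room for favouring an arm.

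The step from omission to error does not stand. No stated rule produces a wrong result. The argument for unequal recording reads a care transfer as an observation schedule. If the sentence is taken for what it is, no participant in either arm has a stated post-operative recording point, and the gap is symmetric. Nor is there a fault in the vasoactive doses: comparing them as randomized gives a valid net effect of adding the block, including any rescue it avoids.

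**Conclusion.** This is missing detail that analysts and investigators ordinarily fill sensibly: a list of block-related, respiratory, haemodynamic and drug-related events, and one recording period for everyone, set when the case report form is built. The plan contains no instruction that would have to be reversed.

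The quantified harm rests on assumptions. Bias between arms is 0 to 3 points at an assumed 10% event rate, grows or shrinks in proportion to that rate, and is zero if events are found equally well outside PACU. The one-event sensitivity and the 8.8% upper limit for 0/40 are properties of 40 per arm and would be the same with a full definition.

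The primary outcome, success of surgical anesthesia, and the trial's objective do not depend on the adverse-event definition. A reader of the results should look for the event list and window actually used, and should not take a non-significant comparison at this size as evidence of safety. That is a caution for interpretation, and no amendment follows.

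### Cheap improvement: open the envelope after the shared IC block, so that the operator does not place it knowing the arm

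*Combined protocol and SAP*

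**What the plan says.** The Objective is to learn whether a supplementary T2 TPVB improves on a cervical-brachial plexus block. Under Methods, "The primary outcome is the success rate of surgical anesthesia".

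On timing, Randomization and blinding describes "sequentially numbered, opaque, sealed envelopes to conceal the sequence until the intervention is assigned" and then states: "The envelopes will be opened sequentially before the nerve block is performed". On blinding, the same section says that "the nerve block intervention cannot be blinded from participants and staff implementing the intervention", and that "only the outcome assessor and data statistician will be kept blinded to the randomized allocation and intervention".

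Interventions adds two facts. First, "The entire nerve block procedure of all the participants will be performed by the same anesthesiologist". Second, for the ICTP arm, "On the basis of IC block, T2 TPVB will then be performed". The IC technique is specified in some detail: ultrasound guidance, an in-plane approach with the whole needle shaft in view, named injection sites, and fixed volumes and concentrations. The first check of block quality comes after all blocks are finished: "Twenty minutes later, after the sensory block assessed, the participant will be transferred to the operating room".

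**The concern.** The trial estimates the increment from one added block, so the IC block is common background and should be delivered identically in both arms. As written, the operator knows the arm before starting it. Someone who knows that a further block will follow, or that none will, may differ in how readily the needle is repositioned, how long is spent, or how imperfect a spread is accepted. None of this need be deliberate.

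If that happened, the arms would differ in more than the TPVB. Success of surgical anesthesia and sensory block depend on both components, so the difference would be counted as a TPVB effect or would offset one. A blinded assessor would record it faithfully, because the difference would lie in the block itself. An intention-to-treat comparison could not separate it afterwards.

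The plan treats the lack of operator blinding as unavoidable. That is right for the TPVB. It is not right for the IC block, which is finished before the two arms diverge.

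**Working it through.** **1. Order of events.** Setting Randomization and blinding beside Interventions gives:

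- envelope opened, allocation known to implementing staff;
- IC block (interscalene, then superficial cervical plexus), both arms;
- T2 TPVB, ICTP arm only;
- supine position, then sensory assessment at 20 minutes.

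The envelope sentence refers to the whole procedure, since the same sections use the term nerve block for the full intervention. Nothing delays the opening until the IC block is complete, and the IC block is not checked separately before the arm is known. The documents do not say who opens the envelope, but they do say that implementing staff are not blinded.

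**2. The plan's own figure.** Methods gives a total of 80, which at 1:1 is 80 / 2 = 40 per arm. It cannot be re-derived, because no success rates, power or sidedness are given. It is used here only for the arm size.

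**3. Illustration.** From the documents: 40 per arm, significance level 0.05, chi-square or Fisher's exact test. Assumed: a two-sided test, no continuity correction, the success rates, and the size of any shift.

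With a successes in ICTP and b in IC, the chi-square statistic at 40 per arm reduces to

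X² = 80(a − b)² / [(a + b)(80 − a − b)], significant if above 3.841.

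For example, 28/40 (70%) against 19/40 gives 80 × 81 / (47 × 33) = 6480 / 1551 = 4.18, which is significant. Fisher's test on the same table gives p = 0.069, which is not.

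The chance of a significant result favouring ICTP is the sum, over all pairs with a > b that the test rejects, of Bin(a; 40, p_ICTP) × Bin(b; 40, p_IC).

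*Less care in the IC arm, no TPVB effect, ICTP success 70%:*

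| IC-arm success | Chi-square | Fisher |
|---|---|---|
| 70% (no shift) | 2.4% | 1.4% |
| 65% (5 points lower) | 6.7% | 4.2% |
| 60% (10 points lower) | 15.0% | 10.4% |

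With ICTP success at 60% or 80% instead, a 10-point shift gives 15.5% or 17.6% (chi-square) and 10.7% or 12.3% (Fisher).

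*More care in the IC arm, true TPVB effect present.* Assume 80% success in ICTP and 50% in IC under equal care, a 30-point effect. The same sum is now the power:

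| IC-arm success | Apparent effect | Chi-square | Fisher |
|---|---|---|---|
| 50% (no shift) | 30 points | 81.7% | 74.9% |
| 55% (5 points higher) | 25 points | 67.2% | 58.6% |
| 60% (10 points higher) | 20 points | 49.7% | 40.8% |

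These tables show what a shift would do. They do not show that one is likely, how large it would be, or which way it would go.

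**The case against.** The plan is not in error here. Opening sealed, opaque, numbered envelopes before the intervention serves the purpose the plan gives, which is concealment of the sequence. The limit on blinding is disclosed, and the assessor and statistician are blinded. The IC block is tightly specified and done by one skilled operator, which removes variation between operators and leaves little discretion. Any assumed difference between arms raises or lowers rejection rates, so the figures are no evidence of bias. Greater care in the IC arm, where nothing follows, is at least as natural as less care, and would make the trial conservative.

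Most of this stands, and it sets the weight of the point. It does not remove the point. Final needle position, judgement of spread and time taken remain with an operator who knows the arm, and a single operator's tendency would run through the whole trial.

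A reader might infer that the result could not be attributed to the TPVB, or that the IC blocks will be placed unequally. The documents support neither: attribution fails only if IC quality actually depends on allocation, and nothing shows that it does. Nor is allocation concealment broken, since the envelope stays sealed until it is opened.

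The objection also limits the remedy. Participants and staff remain unblinded once the envelope is open, so later opening closes only the IC-placement route.

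**Conclusion.** This is a cheap improvement, not a flaw that invalidates the trial. The sequence is clear from the text: the operator performs the shared block knowing the arm, and this is avoidable because the IC block precedes the point where treatment differs. The existing safeguards reduce the scope for differential IC quality without eliminating it.

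That the route exists is well supported. Its size and direction are unknown. On the assumed rates, a 5- to 10-point shift against the IC arm would raise false-positive results favouring ICTP from 2.4% to between 6.7% and 15.0% (chi-square), or from 1.4% to between 4.2% and 10.4% (Fisher). A shift of the same size the other way would take 5 to 10 points off a true effect. These figures depend on success rates and shifts that the documents do not give, and should be read as sensitivity only.

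**What to change.** In Randomization and blinding, replace the sentence on opening the envelopes with text such as:

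> Envelopes are opened in numerical order, and for each participant only after both components of the IC block (interscalene and superficial cervical plexus) have been completed. A participant counts as randomized, for the intention-to-treat analysis, when the envelope is opened.

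The second sentence is needed because the Statistical analysis plan includes all participants as randomized, and later opening would otherwise leave unclear the status of someone whose IC block is not completed. State also who opens the envelope.

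Have the TPVB equipment ready for every participant, so that the set-up does not reveal the arm. Block techniques and doses stay as written, and no rule on further IC injections is proposed.

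The cost is TPVB equipment prepared but unused in about 40 participants, a short pause in the middle of the procedure, and a small change to the workflow of every case. No additional participants are needed.

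### Does the blinding protect the primary outcome when the plan does not say who calls the block failed during surgery?

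*Combined protocol and SAP*

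**What the plan says.** Under the heading on randomization and blinding, the protocol accepts that "the nerve block intervention cannot be blinded from participants and staff implementing the intervention". It therefore restricts masking to two roles: "only the outcome assessor and data statistician will be kept blinded to the randomized allocation and intervention". The one physical step it describes is this: "The envelope will be resealed after confirming the allocation".

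The interventions section adds that "The entire nerve block procedure of all the participants will be performed by the same anesthesiologist". A sensory test follows the block: "Twenty minutes later, after the sensory block assessed, the participant will be transferred to the operating room". In theatre, "The anesthetic effects will be assessed since the operation begin: 1) if it is successful, the operation will be continued"; otherwise, "if it is failed, the operation will be paused and remifentanil will be given intravenous". Neither sentence names a role, and neither says what counts as failure.

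The methods section makes the success rate of surgical anesthesia the primary outcome without defining success. It lists among the secondary outcomes the "proportion of participants who need supplementary anesthesia (intravenous remifentanyl or conversion to general anesthesia").

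**The concern.** The failed call appears to settle the primary outcome, and it also starts remifentanil, so it drives the supplementary-anesthesia outcome as well. It is a judgement about an awake patient with no written threshold. Masking helps only if the masked person makes it. If the anesthesiologist who placed the block, or anyone else who knows the arm, decides that the block has failed, the assessor merely records a decision already taken. A rater who expects the extra block to work might then pass borderline cases in one arm and fail them in the other. With about 40 patients per arm, a few such calls could matter. The plan also does not say whether the assessor stays away during the block, or whether the additional injection site is hidden.

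**Working it through.** **Reading the sections together.**

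| Question | What the document gives |
|---|---|
| Is an outcome assessor masked? | Yes, to allocation and to intervention (randomization and blinding) |
| Is that role separate from those giving the block? | Yes, the same paragraph treats them as different people |
| What is the primary outcome? | Success of surgical anesthesia (methods) |
| Who judges it in theatre? | Not stated (interventions) |
| Is the judgement given to unmasked staff anywhere? | No |
| What defines failure? | Not stated; participant satisfaction enters only two minutes after remifentanil has begun |

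The sections are compatible. A person titled outcome assessor would normally assess the primary outcome, and no sentence points to anyone else.

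**Scale, on assumed inputs.** The document gives a total of 80, 1:1 allocation, a significance level of 0.05, and a chi-square or Fisher test. That makes 80/2 = 40 per arm. The total of 80 cannot be reproduced, because no success rates or power are given. The rest is assumed:

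- a two-sided test and no true effect;
- common success p of 70, 80 or 90%;
- a share f of calls that are borderline and are decided by the arm the rater believes in;
- a probability g that this belief is right.

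Borderline patients are called successes with probability g in the ICTP arm and 1 − g in the IC arm. The bias on the difference is f·g − f(1 − g) = f(2g − 1), split evenly as p ± f(2g − 1)/2. For f = 0.10 and g = 0.80, this is 0.10 × 0.60 = 0.06. At p = 0.80 the arms become 0.83 and 0.77.

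Exact enumeration of two binomial arms of 40 gives these false-positive rates, listed for p = 70, 80, 90%:

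| f | g | Bias (points) | Chi-square, Fisher if an expected count is below 5 | Fisher throughout |
|---|---|---|---|---|
| any | 0.50 | 0 | 0.048, 0.050, 0.026 | 0.028, 0.028, 0.017 |
| 5% | 0.80 | 3.0 | 0.058, 0.063, 0.041 | 0.035, 0.037, 0.028 |
| 5% | 0.95 | 4.5 | 0.070, 0.079, 0.061 | 0.044, 0.048, 0.043 |
| 10% | 0.65 | 3.0 | 0.058, 0.063, 0.041 | 0.035, 0.037, 0.028 |
| 10% | 0.80 | 6.0 | 0.087, 0.102, 0.090 | 0.056, 0.065, 0.066 |
| 10% | 0.95 | 9.0 | 0.138, 0.171, 0.181 | 0.094, 0.116, 0.145 |

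A rater who simply knows the arm has g = 1, and the bias equals f. At f = 5% and p = 80%, Fisher's test then rejects in 0.053 of trials, just above nominal. Larger f with g = 1 goes beyond the last row.

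The first row matters most. A masked rater guesses at chance, so g = 0.50 and f(2g − 1) = 0 whatever the share of borderline calls. The lower rows describe a trial in which the stated masking does not reach the call.

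**The case for a change.** The strongest case for a change is that the reader cannot tell who makes the call. If the masked assessor makes it, one sentence would say so; if not, the blinding statement promises more protection than it gives. An unnamed rater and an undefined endpoint compound each other, and the lower rows of the table are not trivial. The wording gap stands, and so does the lack of a definition of success. That second point, however, concerns the endpoint and would remain under perfect masking.

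The rest carries less weight.

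- The harmful scenario needs an unmasked person to make the call, which the document nowhere says.
- Assigning the call to a particular masked person, or withholding the sensory result from that person, would settle who starts rescue and with what information. In this protocol the same judgement pauses surgery and begins remifentanil, so that is a matter of clinical management and not for a statistical review to decide.
- Covering the neck would hide nothing about allocation, since both arms receive the interscalene and cervical plexus block. Only the T2-T3 site differs, and the document does not indicate that it is in view once the patient is in the beach-chair position.
- Nothing shows that the sensory test reveals the arm.

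**Conclusion.** No change to the plan is needed. This is a gap in a short protocol that a competent team fills in the obvious way: the masked assessor judges the outcome, and success means needing neither remifentanil nor conversion to general anesthesia, which is how the methods and interventions sections read together. On that reading the masking reaches the primary outcome and the supplementary-anesthesia outcome is its complement.

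Any bias is of unknown and possibly negligible size. The illustration runs from none, with a masked rater, to a 9-point bias and a false-positive rate of 9 to 18% in the last row of the table. Every rate behind it is an assumption; only the sample size, allocation ratio, significance level and choice of tests come from the document. Further masking text would also leave untouched the more certain route for bias: participants are awake and know what they received, so any call that draws on their report carries that knowledge whoever records it. The conclusion would differ if the document gave the failed call to someone who knows the arm; it does not.

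### The blinding rule leaves out the operating surgeon and scrub staff for no stated reason, although the surgeon supplies the stimulus against which the primary outcome is judged

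*Combined protocol and SAP*

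**What the plan says.** Randomization and blinding states that "only the outcome assessor and data statistician will be kept blinded to the randomized allocation and intervention". The justification is that the block "cannot be blinded from participants and staff implementing the intervention". Allocation is held in sealed envelopes, opened just before the block and resealed once the arm is confirmed.

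Under Interventions, every block "will be performed by the same anesthesiologist, who is skilled in performing ultrasound-guided regional anesthesia". The arms share the interscalene and superficial cervical plexus blocks; the ICTP arm adds a T2 paravertebral injection of 10 ml of 0.25% ropivacaine. The order of events is: "Twenty minutes later, after the sensory block assessed, the participant will be transferred to the operating room and placed in a beach-chair position". The participant then receives 1 mg midazolam, and general anesthesia is used only on conversion. Anesthetic effect is assessed from the start of surgery, and "if it is failed, the operation will be paused and remifentanil will be given intravenous".

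Methods names the success rate of surgical anesthesia as the primary outcome, in patients "referred for anterior approach proximal humeral fracture surgery". The total sample is 80, allocated 1:1. No role is described for the surgeon or scrub staff in relation to blinding, and surgical handling is not standardized.

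**The concern.** The word *only* makes the list of blinded people exhaustive, but the reason attached to it explains the exclusion of just two groups: participants and those giving the block. The surgeon and scrub staff belong to neither.

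This matters because of how the primary outcome arises. Whether a lightly sedated participant tolerates surgery depends on the block and on the surgical stimulus: retraction, dissection and pace. The surgeon controls the second. The protocol's Background already describes brachial plus cervical plexus block as probably not enough for this surgery, so a surgeon who knew the arm could hold a prior expectation about the IC group and operate accordingly.

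Blinding the assessor protects how a reaction is scored. It does not protect the stimulus that produced the reaction. Allocation concealment and intention-to-treat analysis do not help either, because the influence arises after allocation. If handling differed by arm, the comparison would no longer isolate the added paravertebral block.

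**Working it through.** **1. The exclusion set against its reason.**

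| Group | Covered by the stated reason? | Blinded under the rule? |
|---|---|---|
| Participant | Yes | No |
| Anesthesiologist giving the block | Yes | No |
| Operating surgeon, scrub staff | No | Not listed |
| Outcome assessor | Not applicable | Yes |
| Statistician | Not applicable | Yes |

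**2. Does any described step require the surgeon to know the arm?** The block is given by one anesthesiologist. The block, the 20-minute wait and the sensory test are complete before the move to the operating room. The envelope is resealed. The visible difference between arms is a puncture in the upper back, while surgery is anterior with the participant in the beach-chair position. No step depends on the surgeon's knowledge, and none prevents it.

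**3. Is there a plan figure to reproduce?** The only related figure is the total of 80, and no success rates, power or dropout are given with it. It cannot be reproduced, and this point does not dispute it.

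**4. Sensitivity of the comparison at this size.**

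Inputs from the documents: 80/2 = 40 per arm; significance level 0.05 and chi-square or Fisher's exact test (Statistical analysis plan). Assumptions: two-sided testing, all success rates, and all handling shifts.

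Method: with X successes in IC ~ Bin(40, p_IC) and Y in ICTP ~ Bin(40, p_ICTP), the rejection probability is Σ P(X = i)·P(Y = j) over all 41 × 41 = 1,681 tables with p ≤ 0.05. Results are shown as Fisher / uncorrected chi-square.

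*(a) A real benefit, with gentler handling in the IC arm* (ICTP 90%):

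| IC success | Shift | Power |
|---|---|---|
| 65% | none | 0.717 / 0.793 |
| 70% | +5 points | 0.534 / 0.632 |
| 75% | +10 points | 0.334 / 0.436 |

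*(b) No true block effect, success raised in one arm by handling* (base rate 50% to 80%, rejection in either direction):

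| Shift | Fisher | Chi-square |
|---|---|---|
| none | 0.028–0.033 | 0.048–0.057 |
| 5 points | 0.046–0.055 | 0.075–0.092 |
| 10 points | 0.105–0.162 | 0.152–0.247 |

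A 5-point shift is 0.05 × 40 = 2 participants and a 10-point shift is 4. The tables show that a trial of 40 per arm is sensitive to small differential shifts. Any source of a shift of that size would give the same numbers, so they do not measure this particular problem.

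**The case against.** **Knowledge of the arm is inferred.** The documents never say that the surgeon learns the allocation. Sealed and resealed envelopes, a single block operator and a block finished before transfer all limit exposure, so the surgeon may be unaware in practice. This stands as a limit on the claim. It does not remove the point, because a rule that lists the only people to be blinded gives no protection to anyone else.

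**A false benefit through early stopping.** A reader might infer that a surgeon who expects the IC block to fail would stop sooner, that the stop would count as failure, and that this would favour ICTP. The documents do not support that. Under Interventions the pause follows a failed assessment, and nowhere does a surgeon's stop define failure. The documented sequence leaves a change in the stimulus itself. If that takes the form of gentler handling in the IC arm, it hides a real benefit and does not create a false one.

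**Blinding may not hold.** A reader might also infer that blinding the surgical team would be easy and complete. The participant knows the arm, is awake and can mention the extra injection. The documents do not say who gives anesthetic care during surgery; if it is the block anesthesiologist, an unblinded colleague works beside the surgeon. This stands, and it is why the fix is qualified and records unblinding.

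**Withholding information has a clinical cost.** Keeping the block record from the whole theatre team would affect perioperative care. This stands, and the fix leaves the record accessible.

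**The figures are not evidence about this trial.** Correct: the base rates, shifts and directions are all assumed.

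**Conclusion.** The point holds in a limited form. The blinding rule is narrower than its own justification requires, and it leaves an avoidable route to bias in a primary outcome judged during surgery, one that assessor blinding cannot close. The documents do not show that the surgeon knows the arm, and they give neither size nor direction for any handling effect.

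The conclusion rests on two inferences: that staff outside an exhaustive list are unprotected, and that surgical handling affects whether a lightly sedated participant tolerates the operation. Under assumed rates, a 10-point shift could more than halve power in the Fisher calculation (0.717 to 0.334) or, with no true effect, raise the rejection rate to 0.105–0.247 across both tests. These are illustrations of sensitivity at 40 per arm. Because the remedy is cheap, the change should be made.

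**What to change.** Amend the blinding sentence under Randomization and blinding to add that the operating surgeon and scrub staff will also, as far as possible, be kept unaware of allocation. To carry this out:

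- the surgeon and scrub staff are not present for the block;
- the same dressings are placed on the neck and upper back in both arms;
- participants and block staff are asked not to disclose the arm;
- the surgeon's guess of the arm, and any unblinding, are recorded at the end of surgery.

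State also that the full block and local anesthetic record remains available to the anesthesia team and to anyone who needs it for care.

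The cost is an extra dressing, a request for non-disclosure and one question to the surgeon. The sample size and the analysis are unchanged. Blinding may be imperfect because the participant is awake; the recorded guesses and unblinding events would show how far it held.
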